10.5.3 Predictive values and accuracy

Secondary efficacy will be analysed using positive predictive values, negative predictive values and accuracy for each of the three readers. Computation of the values is shown in the section 9.2.1

10.5.4 Imaging analysis

Imaging will be analysed in terms of inter reader variability and intra reader variability based on Fleiss' kappa statistics and Cohen's kappa statistics respectively. If normality assumption is not met or there is zero agreement in either negative or positive result by a reader or readers, Brennan-Prediger adjustment will be applied.

10.6 Interim Analysis

No interim analysis will be conducted for this study.

10.7 Handling of Missing Data, Outliers and Visit Windows

10.7.1 Missing Data

Missing test results or assessments will not be imputed because missing data is not expected for efficacy outcomes which involve the standard of truth (Section 5.2).

If the start or stop date (or time) for AEs and concomitant medication is incomplete or missing, then a worst-case scenario will be applied for the allocation of an AE or medication. The corresponding listings will always show the original date and time information.

10.7.2 Outliers

In general, outliers should not be excluded purely on the basis of their extreme values, but rather for specified reasons. Such data may be excluded from the analysis at the discretion of the sponsor.

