### **5.3 Blinding**

This is an open-label study.

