### **8.2.2.5 Independent Central Review of PET/CT Images**

A blinded central review of the Zr-TLX250 PET/CT images will be undertaken by an Independent Review Committee (IRC) consisting of 3 experienced reviewers not involved in the conduct of the trial. Reviewers will be independent of the study and without affiliation to the trial Sponsor. They will be blinded with regard to institution, histopathological diagnosis and clinical data. The central PET/CT reviewers will be asked to evaluate both kidneys and the link to the actually operated kidney will be done on the basis of the local pathology report retrospectively. This evaluation will be based on PET/CT images (low dose CT proportion without contrast) only.

Image sets covering extra-renal body regions will have all assessments conducted in the same way by blinded readers. The readers will localise the region within the body of the lesion of interest and then identify it as PET positive or PET negative, based on comparative regional uptake of activity. The readers will be blinded to the histology information on the tissue in question. In the event of multiple non-target lesions, the largest 2 lesions as determined by longest diameter, in each organ, will be evaluated for PET response.

Image data analyses will be performed by a central image core lab. Qualitative visual analysis (presence or absence of localised Zr-TLX250 uptake inside or in vicinity of the target lesion, as seen on contrast-enhanced pre-BL imaging), will be used to assess test performance of Zr-TLX250

PET/CT imaging to non-invasively detect ccRCC, using histological results from the central histological reference laboratory as standard of truth.

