9.2.2 Standardised Uptake Value (SUV)

⁸⁹Zr-TLX250 SUVs will be determined for each tumour lesion. Receiver operating characteristics (ROC) will be analysed, to identify a SUV cut-off value, most appropriate to discriminate between ccRCC or non-ccRCC as evidenced by central histology results.

$$\text{SUV} = C_{\text{image}} / (\text{injected dose} / \text{body weight})$$

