10.7.3 Visit Windows

In general, analyses will not exclude patient data simply due to the patient's failure to comply with the scheduled time/visit. The responsible investigators will decide whether, and to which nominal time points, to include off-window measures, if any, for descriptive summaries of the data.

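### SAP 10.7.2 lets the sponsor exclude outliers at its discretion, with no listed reasons, deadline or blinding to histology; this exposes the SUV cut-off and, less so, the laboratory summaries

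*SAP*

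**What the plan says.** On outliers, SAP 10.7.2 has two sentences. The first is a restraint: "In general, outliers should not be excluded purely on the basis of their extreme values, but rather for specified reasons". The second is a permission: "Such data may be excluded from the analysis at the discretion of the sponsor".

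On timing, SAP 10.7.3 starts from retention: "In general, analyses will not exclude patient data simply due to" a missed visit time. It then delegates: "The responsible investigators will decide whether, and to which nominal time points, to include off-window measures, if any, for descriptive summaries of the data".

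The analysis most open to the first clause is in SAP 9.2.2, where ROC analysis is used "to identify a SUV cut-off value, most appropriate to discriminate between ccRCC or non-ccRCC", judged against central histology. SAP 10.5.2 adds that this is done for each reader, giving three cut-offs with their sensitivities and specificities. SAP 10.4.2 summarises laboratory data and tests change from baseline with a Wilcoxon signed-rank test. SAP 9.2.7 correlates SUV with CAIX expression.

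On blinding, Protocol 5.3 says: "This is an open-label study". Of the central PET/CT readers, Protocol 8.2.2.5 says: "They will be blinded with regard to institution, histopathological diagnosis and clinical data".

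**The concern.** The restraint in 10.7.2 depends on a list of reasons that neither document contains, so in practice the permission decides. Nothing says who at the sponsor decides, when, or with what information in view. Nothing requires the result to be shown without the exclusions.

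This matters most for the SUV cut-off, which is estimated from the same data that would be trimmed. An unusually high SUV in a non-ccRCC lesion is a natural candidate for the label of outlier, and it is also a false positive for any cut-off below it. Removing it shrinks the denominator of specificity by one and leaves the true negatives as they were. A few such decisions, taken with histology known, would make the cut-off look better than it is. The point is the opportunity for bias that the text leaves open, not any presumed intent.

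**Working it through.** **Step 1: look for a limit elsewhere in the documents.**

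- Definition of an outlier: none in the SAP or protocol.
- List of acceptable reasons: none. SAP 10.7.2 refers to reasons but gives none.
- Deadline: Protocol 9.2 has the SAP approved before analysis starts, and Protocol 9.2.3 places analysis after database lock. Neither dates the exclusion decisions, and the approved SAP itself carries the discretion.
- Blinding: the statement in Protocol 8.2.2.5 covers the image readers. It protects the reads, not a later exclusion by the sponsor.
- Analysis with and without exclusions: not required.
- Traceability: SAP 10.1 has all data listed, and SAP 10.5.2 and 10.4.2 put SUV and laboratory data in listings. An exclusion could therefore be found afterwards.

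**Step 2: how far each clause reaches.**

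| Result | Sponsor outlier clause | Investigator off-window clause |
|---|---|---|
| Co-primary and cT1a sensitivity/specificity | Effectively none: a yes/no read has no extreme value, and FAS membership is set by evaluable PET and confirmed histology (SAP 8.1) | None |
| SUV cut-off, SUV-CAIX correlation | Yes | None: SUV comes from one scan |
| Laboratory summaries | Yes, weaker: a rank test limits the pull of extremes | Yes, by-visit descriptive tables |
| Vital signs and ECG by time point | Possible | Yes, by-visit descriptive tables |

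**Step 3: size for the SUV cut-off.** The documents give no figure to reproduce, so this is an illustration.

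Inputs from SAP 7: 70% cT1a with 34% non-ccRCC, and 30% cT1b with 17% non-ccRCC. Inputs for N: 252 (Protocol 9.3) and 300 (SAP 5.1 and 6).

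Non-ccRCC share = 0.70 × 0.34 + 0.30 × 0.17 = 0.238 + 0.051 = 0.289.

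- N = 252: 252 × 0.289 = 72.8, about 73 non-ccRCC.
- N = 300: 300 × 0.289 = 86.7, about 87 non-ccRCC.

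Assumed, not in the documents: 61 of 73 (or 73 of 87) non-ccRCC lesions fall below the SUV cut-off, and the k highest non-ccRCC SUVs, all above it, are dropped. Specificity is then TN / (n − k).

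| k dropped | N = 252 | N = 300 |
|---|---|---|
| 0 | 61/73 = 83.6% | 73/87 = 83.9% |
| 3 | 61/70 = 87.1% | 73/84 = 86.9% |
| 5 | 61/68 = 89.7% | 73/82 = 89.0% |

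The rise is 3.6 and 6.1 points at N = 252, and 3.0 and 5.1 points at N = 300.

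**Step 4: the same thing on the AUC scale.** In 3,000 simulated trials with 179 ccRCC and 73 non-ccRCC lesions (252 − 73 = 179), normally distributed SUVs and a true AUC of 0.90 (both assumed), the mean AUC goes from 0.900 to 0.921 with the 3 highest non-ccRCC values dropped, and to 0.931 with 5 dropped.

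**The case against.** The strongest reply is that 10.7.2 is not an open licence. Its first sentence advises against removing values merely for being extreme, and the second can be read as applying only where a stated reason exists. On that reading the defect is an unwritten list, and the scenario in the working is what the SAP warns against. This stands in part: the scenario is a worst case. It does not close the gap, because a condition with no content cannot be checked and the permission names no other limit.

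The stakes are also modest. The protocol synopsis treats the secondary variables other than reader variability as descriptive, no success criterion attaches to the SUV cut-off, and the CAIX correlation is exploratory. All data are listed. Protocol 8.8.2.3 has clinically relevant abnormal laboratory results recorded as adverse events as well, so an important extreme value would not vanish from the safety record. All of this stands and lowers the priority.

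Three stronger readings are tempting, and the documents do not support them:

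- That the primary result is at risk. It rests on yes/no reads by blinded readers, with the FAS defined separately.
- That investigators can shift SUV results through the visit-window clause. That clause is confined to descriptive summaries, its default is to keep data, and SUV has a single imaging time point.
- That the open-label design makes exclusions unblinded. The trial has one arm, so there is no allocation to reveal. The documents do not say when the sponsor sees SUV linked to histology; the gap is that they do not rule it out before exclusions are decided.

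**Conclusion.** The point holds in a limited form. SAP 10.7.2 ties outlier exclusion to reasons that neither document states and leaves the decision to the sponsor, with no requirement that it precede database lock or be made without sight of histology. The data-derived SUV cut-off is the main result exposed, followed by the exploratory SUV-CAIX correlation and, less so, the laboratory summaries. The confirmatory endpoints are effectively untouched.

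Removing 3 to 5 high non-ccRCC SUVs would lift apparent SUV specificity by about 3 to 6 points. That size rests on an assumed starting specificity near 84%, on the SAP's planning mix, and on one-sided removal from the non-ccRCC group. It shows how sensitive the result is to a few exclusions, not the bias to be expected.

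The off-window discretion in SAP 10.7.3 is a separate, smaller matter that bears on by-visit safety tables only. This is a worthwhile low-cost improvement, not a threat to the trial's main conclusion.

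**What to change.** In SAP 10.7.2, delete the discretion sentence and state that:

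- all recorded values are analysed;
- a value is excluded only for a documented measurement or data error, such as an assay failure or a data-entry error;
- each such decision is made before database lock by staff unaware of histology and central reads;
- every exclusion is listed with its reason;
- SUV and laboratory results are shown with and without the excluded values.

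In SAP 10.7.3, replace investigator choice with a fixed rule that assigns each off-window value to the nearest nominal visit.

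The cost is a few sentences of SAP text plus a little more analysis and documentation. No new data are needed, and timelines are not affected.

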10.7.3 Visit Windows

In general, analyses will not exclude patient data simply due to the patient's failure to comply with the scheduled time/visit. The responsible investigators will decide whether, and to which nominal time points, to include off-window measures, if any, for descriptive summaries of the data.

11 TABLES, LISTINGS AND FIGURES

11.1 Tables

Tables will be produced for all analyses carried out on variables of the study. Names of tables will be provided above the table. Tables will be named according to the contents as prescribed by ICH guidelines.

11.2 Listings

Data listings will be provided and numbered in accordance to appropriate regulations.

11.3 Figures

Figures will be provided where it is necessary.

[figure not shown]
